### Decision to Proceed to Comparative Analyses

The decision to move forward with the comparative analysis for either the acute MI or the stroke outcome will be made after assessment of covariate balance across treatment groups (eg, based on an absolute standardized mean difference of > 0.10 for covariates included in the PS model, and adequate overlap in the PS across treatment arms), null findings for the final set of negative control outcomes (ie, posterior probability > 90% that the level of bias is less than 10% of the null), and sufficient sample size to detect a risk ratio of 2.0 or greater. For the relatively rate outcome of acute MI, a total of 15,000 patients in each comparator arm will be needed in order to detect a risk ratio of 2.0 or greater, assuming 80% power and a background rate of acute MI of 0.15 per 100 person-years. In contrast, for the outcome of stroke, 3,750 patients will be required in each treatment arm to detect a risk of 2.0 or greater, assuming 80% power and a background rate of stroke of 0.60 per 100 peson-years.

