### 8.7.2 Planned Method of Analysis

#### 8.7.2.1 General Considerations

All descriptive and comparative analyses will be undertaken in the interactive Casual Studio application. Characterization of patient populations by baseline characteristics is easily accommodated by the software. In addition, the application allows for the estimation of the cumulative risk of a right censored outcome that may be subject to dependent (right) censoring. Overall estimates of risk at various time points, as well as estimates of risk stratified by medical history, demographic characteristics, and medication usage can be presented in both tabular and graphical formats.

A major challenge in observational comparative analyses is the lack of exchangeability, with baseline characteristics that may be unbalanced between study groups and potential differential drop-out across the two arms of the study. Causal Studio is a tool designed to address exchangeability in observational studies. More specifically, the application allows for the estimation of the cumulative risk of a right-censored counterfactual outcome that may be subject to dependent censoring and confounding. Causal Studio is structured as follows: (1) based on user-specified propensity score models and/or censoring models, generate inverse probability of treatment weights (IPTWs) and inverse probability of censoring weights (IPCWs); (2) provide diagnostics (eg, distribution of the propensity score, by treatment groups; and, standardized mean differences between treatment groups for categorical and continuous variables) that enable the user to assess whether the analyses should proceed to the comparative stage, and, if appropriate, (3) execute the structural (ie, weighted) model to estimate the effect of treatment on the outcome. For our purpose, we will use Causal Studio to separately compare the risk of acute MI and stroke in new users of erenumab-acoe versus new users of each of the other three new user comparator cohorts.

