### **Comparability Analyses**

### Estimating the Propensity Score

Next, a linear-logistic model for the conditional probability of treatment,  $Pr(A_i=a|L_i)$ , where  $L_i$  is a vector of measured confounders of the exposure and the outcome, as well as risk factors for the outcome, will be fit (Brookhart et al, 2006). The conditional probability of treatment given a set of covariates is commonly referred to as the propensity score (PS).

For the first set of comparability analyses, overlap of the propensity score across treatment groups will be evaluated. Non-overlap in the PS will be addressed with trimming of subjects at the extremes of the PS distribution. In addition, the mean standardized difference for all variables included in the PS model will be estimated. An absolute mean standardized difference > 0.1 for a given confounder or risk factor for the outcome will be used as a measure of potential imbalance (Austin, 2009; Austin et al. 2007). Covariates in the propensity score model with an absolute standardized difference > 0.1 will be examined for potential inclusion in the outcome model or will be used as evidence of insufficient overlap in the distribution of baseline characteristics across treatment groups. Using PS overlap and cut points for the mean standardized difference to make decisions about cohort comparability are part of an iterative process that potentially involves trimming of subjects (because of poor overlap in the PS) and accounting for confounders in the outcome model rather than the exposure model. As such, this process provides guidance on whether cohorts are comparable and contributes additional information to the body of evidence used to determine whether comparative analyses should be initiated or not.

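### The go/no-go rule writes the covariate-balance criterion in the wrong direction (absolute SMD > 0.10), contradicting the propensity-score section, where > 0.1 marks imbalance

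*Protocol*

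**What the plan says.** Two subsections of Protocol Section 8.7.2.4 use the same cut-off.

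- **Decision to Proceed to Comparative Analyses.** The decision to go ahead "will be made after assessment of covariate balance across treatment groups", and a parenthesis introduced by an e.g. explains how balance is judged: "based on an absolute standardized mean difference of > 0.10 for covariates included in the PS model", joined by an *and* to "adequate overlap in the PS across treatment arms". The sentence then adds null findings for the negative control outcomes (posterior probability above 90% of acceptable bias) and enough patients to detect a risk ratio of 2.0.
- **Estimating the Propensity Score.** On the meaning of a large value, this subsection reads: "absolute mean standardized difference > 0.1 for a given confounder or risk factor for the outcome will be used as a measure of potential imbalance". On what then happens to such covariates, it reads: "standardized difference > 0.1 will be examined for potential inclusion in the outcome model or will be used as evidence of insufficient overlap". The subsection describes the process as iterative and as guidance that adds to the evidence.

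The Abstract and the opening of Section 8.7.2.4 describe the same decision without a numerical cut-off for the standardized mean difference (SMD).

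**The concern.** The Decision subsection is where an analyst will look for the rule that opens or closes each comparative analysis. Each item next to the SMD is phrased as something to be achieved. An SMD above 0.10, placed in that list, reads as something to be achieved too, although the earlier subsection treats it as a warning sign.

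The Abstract says that analyses will go ahead only in treatment pairs where comparability and sufficient sample size are achieved. The negative-control subsection expects that initiators of newer agents may have more severe disease than users of the older preventives. Raw imbalance is therefore plausible, and the balance criterion may well come into play. A prespecified criterion of this kind should be readable in only one direction.

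**Working it through.** A cut-off is a choice and cannot be re-derived from inputs, so the check is a comparison of texts.

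**1. Role of each item in the Decision subsection**

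| Item | As written | Type |
|---|---|---|
| SMD of treatment-model covariates | > 0.10 | reads as a condition to meet |
| Propensity-score overlap | adequate | condition to meet |
| Negative controls | posterior probability > 90% | condition to meet |
| Sample size | enough to detect a risk ratio of 2.0 | condition to meet |

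The SMD and the overlap item stand in the same parenthesis, joined by *and*. Nothing in the sentence marks the first as a failure flag and the second as a pass condition.

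**2. The same cut-off in the propensity-score subsection**

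- Meaning: "difference > 0.1 for a given confounder or risk factor for the outcome will be used as a measure of potential imbalance".
- Consequence: the covariate is considered for the outcome model, or it counts against comparability.

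If above 0.1 marks imbalance, the matching pass condition is its complement, an absolute SMD of 0.10 or less. The Decision subsection gives the other side of the cut-off.

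**3. Which sample the SMD is taken in**

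- The propensity-score subsection says only that "the mean standardized difference for all variables included in the PS model will be estimated"; neither it nor the Decision subsection says before or after weighting.
- Section 8.7.2.1 gives the software's order: first the treatment and censoring weights, then diagnostics including SMDs to judge whether to go on, then the weighted outcome model. This suggests weighted SMDs without stating it.
- The negative-control subsection, also ahead of the decision, controls for measured confounders with inverse probability weights.

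No passage says that the SMD is unweighted.

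**4. Scale of the cut-off**

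For a binary covariate with prevalences p0 and p1,

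SMD = (p1 − p0) / sqrt{[p1(1 − p1) + p0(1 − p0)] / 2}.

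- p0 = 0.100, p1 = 0.132: 0.032 / sqrt[(0.1146 + 0.0900)/2] = 0.032 / 0.320 = 0.10.
- p0 = 0.200, p1 = 0.2414: 0.0414 / sqrt[(0.1831 + 0.1600)/2] = 0.0414 / 0.414 = 0.10.

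So the cut-off separates pairs that differ by less than about 10.0% versus 13.2%, or 20.0% versus 24.1%, from pairs that differ by more.

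**5. Reach**

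Baseline balance belongs to a treatment pair. There are three pairs (erenumab against other CGRP antibodies, anti-epileptics and onabotulinumtoxinA), and the a priori treatment-model covariates in Appendix D are not listed separately by outcome. That makes three balance assessments. Acute MI and stroke differ in the stated sample-size requirement: 15,000 and 3,750 per arm.

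**The case against.** The strongest defence is that the direction is fixed a page earlier. The propensity-score subsection leaves no doubt that a value above 0.1 is unfavourable, and the Decision sentence speaks of assessing balance. On a lenient reading, its parenthesis only names the flag used in that assessment; it never says in so many words to go ahead when the SMD exceeds 0.10. This stands as far as intent goes: a competent analyst would probably apply the rule correctly. It does not make the sentence right, because its neighbours are all pass conditions.

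It is also fair that the SMD is not a single hard cut-off. The e.g. and the description of an iterative process show that it is one strand of evidence. That limits the consequence of the slip.

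A reader might infer more than the document supports:

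- *That the balance check is made on unweighted data, or that weights enter only under Gated Analyses.* Section 8.7.2.1 puts weight generation before the SMD diagnostics, and the negative-control estimates are already weighted. The sample used for the SMD is simply unstated, which a statistical analysis plan may settle; none is at hand.
- *That the whole decision fails to test the weighted comparison.* The negative-control part uses weighted estimates, so one part does test it.
- *That six separate balance decisions are affected.* Balance is assessed by pair, so there are three.

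**Conclusion.** The point holds for the direction of the threshold. As written, the Decision subsection puts an absolute SMD above 0.10 among the conditions for going ahead, which contradicts the propensity-score subsection. It is a wrong decision criterion on the page, with recoverable intent.

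It would go too far to conclude that the study will let imbalanced pairs through. That requires ignoring the earlier subsection, and the SMD is only one of several parts of the decision. The realistic harm is ambiguity in a prespecified rule covering three treatment pairs. No computed figure in the protocol depends on it.

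The conclusion assumes that the propensity-score subsection states the intended meaning, which its explicit consequence for covariates above 0.1 supports.

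**What to change.** In Decision to Proceed to Comparative Analyses, state the balance condition as an absolute SMD of 0.10 or less for covariates included in the propensity-score (treatment) model. Add that any covariate above 0.10 is handled as under Estimating the Propensity Score: considered for the outcome model, or counted as evidence of insufficient overlap.

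Two cautions on the wording:

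- Keep the condition to treatment-model covariates. Appendix D also lists variables used only in the censoring model, such as vaccinations and screening tests, so applying it to every Appendix D variable would be wrong.
- Do not make it an absolute bar for every covariate. That would remove the existing option of dealing with residual imbalance in the outcome model and would change the method.

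As an optional clarification, say that the SMD is taken in the trimmed, treatment-weighted sample, in line with the step order in Section 8.7.2.1.

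The cost is one sentence, or two with the clarification. No new data or analyses are needed, and the Abstract needs no change because it gives no SMD cut-off.

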### Negative Control Outcome Analyses

Negative control outcome studies are designed to detect and reduce residual bias between treatment groups (Lipsitch et al, 2007, Arnold and Ercumen, 2016). Negative control outcomes are chosen that have no plausible mechanism by which they can be caused by the treatment of interest but do share unmeasured confounders (eg, lifestyle [smoking history, alcohol use], and anthropometric [BMI] variables) with the primary treatment-outcome relation. After controlling for measured confounders, any observed association between the treatment and negative control outcome can be attributed to unmeasured confounding between the groups, rather than a true causal relationship. For example, if the outcome for a comparative safety study is acute MI, the ideal negative control outcomes would share a similar confounding structure as would be hypothesized

for treatment selection (eg, erenumab-aooe vs. other mAbs targeting the CGRP pathway) and the outcome of interest (acute MI). Common outcomes used as negative controls in prior epidemiologic studies of treatments include risks of accidents or hospitalizations for trauma or injury (Dormuth et al, 2009; Brookhart et al, 2007; Jackson et al, 2006).

Selection of migraine preventive treatment is likely affected by many factors associated with a patient's prognosis that can lead to bias when comparing treatment groups in non-interventional settings. Patients initiating newer medications, such as mAbs targeting the CGRP pathway, may have more severe disease and be at higher risk for poor outcomes in comparison to patients initiating other migraine preventive therapies, such as selected SOC migraine preventive medications (anti-epileptics) or onabotulinumtoxinA . It is of interest to understand whether the incidence of clinical outcomes among patients initiating other migraine preventive medications after controlling for measured confounding factors. We will use a negative control study design to investigate this comparability of patients initiating different types of migraine preventive treatments. The results of this analysis will help inform the appropriateness of comparative safety analysis for the two CV outcomes of interest (acute MI and stroke). The negative control outcomes that may be included in the analysis are:

- o Decubitus ulcer
- o Dementia
- o Transfusions
- o Accidents
- Annual wellness visit
- Pelvic exams for cancer screening
- o Influenza vaccine use
- o Mohs surgery

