# Estimating the Cumulative Distribution of a Right-Censored Counterfactual Outcome, Accounting for Informative Censoring

To accommodate informative censoring due to drop-out from a health plan, switching to an alternate medication, or discontinuation of study medication, IPCWs will be estimated. Specifically, a linear-logistic model for the conditional probability of remaining uncensored  $Pr(\Delta_i=1|D_i, A_i)$ , where  $D_i$  is a vector of measured confounders of drop-out / switching / discontinuation and the outcome and  $A_i$  is a discrete random variable denoting exposure to erenumab-aooe (a=1) or other mAbs targeting the CGRP pathway (a=0) for patient i, will be fit. IP censoring weights will then be constructed as:

$$\widehat{W}_i^2 = \frac{1}{\widehat{Pr}(\Delta_i = 1 | D_i, A_i)}$$

Variables to be included in the censoring model will include demographic characteristics, medication usage, disease history, and utilization of medical resources, all of which will be included in the censoring model (see Appendix D). For new users of erenumab-aooe and other mAbs targeting the CGRP pathway, the cumulative incidence curves weighted

by inverse probability of censoring weights provide a valid estimate of the risk for acute MI at various time points, now accounting for informative censoring.

The cumulative incidence curves for acute MI, weighted by the multiple of IPTWs (ie,  $\widehat{W}_i^1$ ) and IPCWs (ie,  $\widehat{W}_i^2$ ), account for both confounding by measured covariates and informative censoring. The full estimating function for the counterfactual cumulative incidence of acute MI is then defined as:

$$\widehat{Pr}(T^a < t) = \frac{1}{n} \sum_{i=1}^{n} \frac{\Delta_i I(T_i < t) I(A_i = a)}{Pr(\Delta_i = 1 | D_i, A_i) \Pr(A_i = a | L_i)}$$

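### The size criterion for the comparative analysis counts unweighted patients, so an MI contrast that only just meets it has less than the stated 80% power once the analysis is weighted

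*Protocol*

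**What the plan says.** Section 8.7.2.4 (Decision to Proceed to Comparative Analyses) requires covariate balance with adequate PS overlap, acceptable negative control results, and "sufficient sample size to detect a risk ratio of 2.0 or greater". It turns the size requirement into patient counts:

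- Acute MI: "a total of 15,000 patients in each comparator arm will be needed".
- Stroke: "3,750 patients will be required in each treatment arm to detect a risk of 2.0 or greater".

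Both counts rest on 80% power, with background rates of 0.15 (MI) and 0.60 (stroke) events per 100 person-years.

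The analysis that this decision admits is described in the same section. On overlap: "Non-overlap in the PS will be addressed with trimming of subjects at the extremes of the PS distribution". The cumulative incidence curves are then "weighted by the multiple of IPTWs" and the censoring weights. The section on negative control outcomes also expects that users of the newer antibodies "may have more severe disease and be at higher risk for poor outcomes in comparison to patients initiating other migraine preventive therapies".

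Neither the size criterion nor Table 3 (Section 8.5) mentions weight variability, effective sample size or a design effect. The protocol does not say whether the count is taken before or after trimming.

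**The concern.** A sample size formula for two unweighted groups describes the precision of an unweighted comparison. With unequal inverse probability weights, the information in an arm is closer to the effective sample size, (Σw)² / Σw², which is never larger than the number of patients. If the threshold has no reserve, a contrast can meet the count and still lack the power that the criterion is meant to secure.

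The criterion exists to prevent uninformative safety comparisons. A null MI result from a contrast that met its size requirement carries more weight with readers than it should if the weighted estimate had noticeably less than 80% power to show a doubling.

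**Working it through.** **Inputs.** Background risks p₁ = 0.0015 (MI) and 0.006 (stroke), risk ratio 2.0, 80% power and the two counts come from Section 8.7.2.4. Alpha 0.05 and equal arms come from Section 8.5. Two-sided testing and 1 person-year per patient are assumptions; neither is stated.

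**Step 1: reproduce the plan's counts.**

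- Event-based (Schoenfeld): 4 × (1.96 + 0.8416)² / (ln 2)² = 65.4, so 66 events. Each patient pair contributes p₁ + 2p₁ = 3p₁ expected events. MI: 66 / (3 × 0.0015) = 14,667 per arm. Stroke: 66 / (3 × 0.006) = 3,667.
- Pooled two-proportion formula: 15,662 (MI) and 3,888 (stroke).

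The stated 15,000 and 3,750 lie between the two. They are unweighted counts at about 1 person-year per patient.

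**Step 2: power at the threshold without weights.** For n per arm,

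z = [ (p₂ − p₁)√n − 1.96√(2p̄q̄) ] / √(p₁q₁ + p₂q₂).

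For MI at n = 15,000: (0.0015 × 122.47 − 0.1313) / 0.0670 = 0.782, which is 78% power. Stroke at 3,750 gives 79%. The event-based formula at 67.5 expected events (22.5 + 45) gives 81%. There is no reserve.

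**Step 3: the same calculation at n / design effect (DE).** The DE values are assumptions.

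| DE | Effective n, MI | Power, MI at 15,000 | Power, stroke at 3,750 |
|---|---|---|---|
| 1.0 | 15,000 | 78% | 79% |
| 1.1 | 13,636 | 74% | 75% |
| 1.25 | 12,000 | 69% | 69% |
| 1.5 | 10,000 | 61% | 61% |
| 2.0 | 7,500 | 49% | 49% |

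Keeping the plan's own standard would need the stated count times DE. At 1.25 that is 15,000 × 1.25 = 18,750 for MI and 3,750 × 1.25 = 4,688 for stroke.

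**Step 4: what DE might arise.** In a simulation with a normally distributed logit PS and equal arms (an illustration, not a figure from the plan), the treatment weights alone gave:

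| PS c-statistic | DE |
|---|---|
| 0.58 | 1.02 |
| 0.63 | 1.07 |
| 0.69 | 1.16 |
| 0.74 | 1.32 |
| 0.78 | 1.59 |
| 0.81 | 2.01 |

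Moderate censoring weights added roughly 0.03 to 0.2.

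**Step 5: projected sizes.** Section 8.5 projects about 20,000 erenumab, 23,000 other antibody and 13,000 onabotulinumtoxinA users, and an anti-epileptic cohort at least as large as erenumab (taken as 20,000). Power for risk ratio 2.0 at 1 person-year per patient:

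| Contrast | DE 1.0 | 1.25 | 1.5 | 2.0 |
|---|---|---|---|---|
| MI, 20,000 vs 23,000 | 91% | 84% | 77% | 65% |
| MI, 20,000 vs 20,000 | 89% | 81% | 73% | 61% |
| Stroke, 20,000 vs 13,000 | >99% | >99% | >99% | 98% |

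With 20,000 per arm, MI power reaches 80% at DE = 20,000 / 15,662 = 1.28. The smallest stroke contrast still has 90% at DE 3. MI against onabotulinumtoxinA fails the existing count, since 13,000 is below 15,000.

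**The case against.** Several points on the other side stand.

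- **The worst cases are less likely to qualify.** The same decision rule requires adequate PS overlap. A DE near 2 goes with c-statistics around 0.8 in the illustration, which means poor overlap. Cohorts that overlap well may lose only a few points of power.
- **Trimming may already be reflected.** Trimming belongs to the comparability work, and the decision comes after it, so the count may be taken after trimming. The text does not settle this. A count after trimming would still ignore weight variability.
- **The expected channelling is not general.** The protocol expects it between the antibodies and the older preventives, not between erenumab and the other antibodies. For the anti-epileptic contrast there is a further reason to expect variable weights: Section 8.2.2.2 excludes prior users of the index anti-epileptics from that cohort but not from the erenumab cohort, while Appendix D puts baseline use of select anti-epileptics in the treatment model. This applies if that term covers the index drugs, as Table 1 does.
- **Follow-up matters at least as much.** At the MI threshold without weighting, power is 49% at 0.5 and 92% at 1.5 person-years per patient. At 1.5 person-years and DE 1.5 it is 78%.
- **Imprecision will be visible.** Risk ratios are reported with 95% confidence intervals.
- **Table 3 is labelled informational.** It does not bind the decision.

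It can also be said that the working details of a size check belong in an analysis plan. That does not remove the point, because the protocol itself fixes the thresholds and states the power attached to them.

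**Conclusion.** The point holds in a limited form. The 15,000 and 3,750 counts carry about 78–81% power for an unweighted comparison. The comparative analysis is weighted, so a contrast that only just meets the count has less than the stated 80%. How much less depends on a DE that the protocol does not give: from a few points at 1.1 to 49% power at 2.0, all at 1 person-year per patient.

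The practical weight falls on MI. At projected sizes, MI drops below 80% power at a DE between about 1.25 and 1.5.

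A reader might infer that the criterion will admit comparisons that miss a true doubling of MI or stroke 30–50% of the time. The documents do not support that. Stroke keeps about 98% power or more up to DE 2 at the projected cohorts. For MI at projected sizes, a miss rate above 30% needs a DE above 1.5, and the overlap requirement makes that less likely. Nor do the documents establish that trimming takes patients away after the count is made.

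**What to change.** In Section 8.7.2.4 (Decision to Proceed to Comparative Analyses), apply the size criterion after trimming and weighting. Compute the effective sample size per arm, (Σw)² / Σw², from the final product of treatment and censoring weights, and require at least 80% power for a risk ratio of 2.0 at those sizes. Because censoring weights change with follow-up, name the time point and use the background risk at that same time point. Optionally, note in Section 8.5 that Table 3 refers to unweighted patients.

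The cost is one extra diagnostic and some wording. Section 8.7.2.1 already has the software generate both sets of weights and show diagnostics before the comparative stage. The downside is that an MI contrast that meets the present count may no longer qualify.

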The naïve, unadjusted cumulative incidence (ie, risk) of hypertension, acute MI, and stroke will be estimated in the following new user cohorts: 1) erenumab-aooe, 2) other mAbs targeting the CGRP pathway, (2) select SOC migraine preventive medications (anti-epileptics), and (3) onabotulinumtoxinA.

Next, the overlap of the propensity score across treatment groups will be evaluated, the mean standardized difference for all variables included in the propensity score model will be assessed, and a determination will be made on whether null findings are or are not estimated for the negative control outcomes chosen for the study. Comparability between erenumab-aooe and each of the other treatment cohorts will be evaluated separately and each of the comparative analyses will be gated. Specifically, the decision to move forward with the comparative analyses for either the acute MI or the stroke outcome will be made after assessment of covariate balance across treatment groups, whether the negative control outcomes showed treatment associations within the accepted bounds around the null, and sufficient sample size to detect a risk ratio of 2.0 or greater. Analyses will proceed only in the treatment pairs where comparability and sufficient sample size are achieved, and not in others.

Based on the comparability analyses and sample size considerations, the risk of acute MI and the risk of stroke will be separately compared across the following three exposure contrasts: (1) erenumab-aooe vs other mAbs targeting the CGRP pathway, (2) erenumab-aooe vs select SOC migraine preventive medications (anti-epileptics), and (3) erenumab-aooe vs. onabotulinumtoxinA. For these gated analyses, we will utilize inverse probability of treatment weights to account for confounding and inverse probability of censoring weights to account for informative censoring.

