#### 8.5 Study Size

Based on recent analyses (Amgen Study 20200218) to evaluate the rate of hypertension in migraine patients, the following number of patients with a migraine preventive treatment were identified within the Marketscan® Early View claims database from May 2018 through January 2020:

- 15212 erenumab-aooe users
- 17239 galcanezumab-gnlm or fremanezumab-vfrm users
- 9242 onabotulinumtoxinA users

These migraine preventive treatment users were required to be 18-64 years of age, have a diagnosis for migraine based on ICD-10-CM diagnosis codes or one prescription order for a triptan/ergot in the prior 12 months, continuous enrollment in the claims database for at least 12 months prior to the index date, and no prior prescription for any medication targeting the CGRP pathway. These counts were generated before the February 2020 approval of eptinezumab-jjmr. Assuming a conservative 3-month growth rate of 15%, the expected number of new users during the study period (17 May 2018 – 31 May 2020) will be ~20 000 new users of erenumab-aooe, ~23 000 new users of other mAbs targeting the CGRP pathway, and ~13 000 new users of onabotulinumtoxinA. While new users of the SOC migraine preventive medications (anti-epileptics) were not evaluated, other analyses in the Optum electronic health record database suggest that this new user cohort will be at least as large as the erenumab-aooe new user cohort.

Table 2 provides the 95% confidence interval estimates for various potential risk estimates of the three cardiovascular outcomes (0.2%, 0.5%, 1%, 3%, 5%, 20%, and

30%) based on the projected sample size described above for erenumab-aooe, other mAbs targeting the CGRP pathway, and onabotulinumtoxinA. The risk of acute MI and stroke is expected to be relatively rare across all new user cohorts, while the risk of hypertension is expected to be common.

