#### Table 2. 95% CI Estimates and Half-widths for a Range of Cardiovascular Outcome Values, Based on a Sample Size of 20 000 Erenumab-aooe Users, 23 000 Users of Other mAbs Targeting the CGRP Pathway and 13 000 Onabotulinumtoxin A Users

	Erenumab-aooe N = 20 000		Other mAbs Targeting the CGRP Pathway N = 23 000		OnabotulinumtoxinsA N = 13 000	
CV Outcome (%)	95% CI	Half-width of Cl	95% CI	Half-width of Cl	95% CI	Half-width of Cl
0.20	0.14, 0.26	0.06	0.14, 0.26	0.06	0.12, 0.28	0.08
0.50	0.40, 0.60	0.10	0.41, 0.59	0.09	0.38, 0.62	0.12
1.00	0.86, 1.14	0.14	0.87, 1.13	0.13	0.83, 1.17	0.17
3.00	2.76, 3.24	0.24	2.78, 3.22	0.22	2.71, 3.29	0.29
5.00	4.70, 5.30	0.30	4.72, 5.28	0.28	4.63, 5.37	0.37
20.0	19.5, 20.6	0.55	19.5, 20.5	0.52	19.3, 20.7	0.69
30.0	29.4, 30.6	0.64	29.4, 30.6	0.59	29.2, 30.8	0.79

Abbreviations: CI: confidence interval; mAbs: monoclonal antibodies; CGRP: calcitonin gene-related peptide

Table 3 provides a range of detectable risk ratios for two outcomes of interest (acute MI and stroke), assuming 80% power, alpha-level of 0.05, and equal number of patients in each medication cohort, if a comparative analysis of the erenumab-aooe cohort to each comparator cohort (other mAbs targeting the CGRP pathway, selected SOC migraine preventive medications (anti-epileptics), or selected onabotulinumtoxinA ) were conducted. This table assumes a background rate of acute MI of 0.15 per 100 PYs and a background rate of stroke of 0.60 per 100 PYs (Gill et al, 2020).

 Table 3. Detectable Risk Ratios for Two Cardiovascular Outcomes

	Total Population in Each Medication Cohort						
Outcome	N = 13 000	N = 17 000	N = 20 000	N = 25 000			
Acute MI	2.10	1.94	1.85	1.75			
Stroke	1.58	1.51	1.46	1.41			

The estimates provided above are for informational purposes only. The final sample size for the study will change due to the criteria applied during the conduct of the protocol.

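### The acute MI size condition is an equal-arm count; at the projected sizes it closes the onabotulinumtoxinA contrast while admitting a pair with about the same power

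*Protocol*

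**What the plan says.** Protocol Section 8.7.2.4 (Decision to Proceed to Comparative Analyses) makes "sufficient sample size to detect a risk ratio of 2.0 or greater" one of the conditions for comparing acute MI or stroke. For MI it states that "a total of 15,000 patients in each comparator arm will be needed in order to detect a risk ratio of 2.0 or greater". The inputs it gives for this count are a power of 80% and an MI rate of 0.15 per 100 person-years in the background. The stroke counterpart is 3,750 per arm at 0.60 per 100 person-years.

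The Abstract (Data Analysis) makes the condition binding: "Analyses will proceed only in the treatment pairs where comparability and sufficient sample size are achieved, and not in others".

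Section 8.5 projects about "20 000 new users of erenumab-aooe, ~23 000 new users of other mAbs targeting the CGRP pathway, and ~13 000 new users of onabotulinumtoxinA". Table 3 in the same section gives detectable risk ratios "assuming 80% power, alpha-level of 0.05, and equal number of patients in each medication cohort". For MI these are 2.10, 1.94, 1.85 and 1.75 at 13,000, 17,000, 20,000 and 25,000 per cohort.

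**The concern.** The criterion is power at a risk ratio of 2.0, which is a property of a pair of arms. The protocol turns it into a minimum count that was derived for two arms of the same size. In one planned MI contrast the comparator is projected at 13,000, below that count, while the erenumab arm, at 20,000, is well above it. The larger arm can make up for the smaller one, but a fixed count gives it no credit.

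The wording could mean the comparator cohort alone or each arm of the pair; 13,000 fails on either reading. What is at stake is a go/no-go decision on one of the three MI safety contrasts named in Section 7.1. It could be dropped as too small on a figure that does not describe it.

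**Working it through.** **Inputs.** Background MI rate 0.15 per 100 person-years, risk ratio 2.0 and 80% power (Section 8.7.2.4); alpha 0.05 and equal cohorts (Section 8.5, Table 3); projected sizes 20,000, 23,000 and 13,000 (Section 8.5). Two points are assumed because the protocol does not state them: a two-sided test, and one person-year per patient. This gives p0 = 0.0015 and p1 = 0.0030. Both assumptions are supported by the fact that they reproduce the protocol's MI figures.

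**Formula (arcsine, two proportions).** h = 2·asin√p1 − 2·asin√p0 = 0.03212. Power = Φ(h·√(n1·n0/(n1+n0)) − 1.96).

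**Reproducing the protocol's figures.**
- Patients per arm, 1:1: 2·((1.96 + 0.8416)/0.03212)² ≈ 15,215 for MI (stated 15,000). The same formula gives about 3,779 for stroke (stated 3,750).
- Detectable MI risk ratio at 13,000, 17,000, 20,000 and 25,000 per arm: 2.097, 1.937, 1.853 and 1.751, which is the MI row of Table 3.

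**Applying it to the pairs at issue (risk ratio 2.0).**

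| Pair | n1·n0/(n1+n0) | Power | Detectable RR | Meets the 15,000 count? |
|---|---|---|---|---|
| 13,000 vs 13,000 | 6,500 | 73.6% | 2.10 | no |
| 15,000 vs 15,000 | 7,500 | 79.4% | 2.01 | yes |
| 20,000 vs 13,000 | 7,879 | 81.4% | 1.98 | no |

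For 20,000 vs 13,000: 0.03212·√7,879 = 2.851; 2.851 − 1.960 = 0.891; Φ(0.891) = 0.814. With 20,000 erenumab users, about 12,000 comparators match the power of 15,000 vs 15,000, and about 12,280 give 80%.

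**Other formulas.**

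| Formula | 20,000 vs 13,000 | 15,000 vs 15,000 |
|---|---|---|
| Pooled z | 79.1% | 78.3% |
| Unpooled z | 83.0% | 78.3% |
| Log risk ratio | 75.9% | 76.6% |
| Schoenfeld | 85.5% | 81.3% |

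Only the log risk ratio ranks the excluded pair lower, by under one point, and it puts both pairs below 80%.

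**Dependence on the projection.** Section 8.5 starts from 15,212 erenumab and 9,242 onabotulinumtoxinA users to January 2020 and assumes 15% growth per three months.
- Two quarters: 15,212·1.15² = 20,118 and 9,242·1.15² = 12,223. Power is 80.0% (arcsine) or 77.5% (pooled z).
- Four months to 31 May 2020: 15,212·1.15^(4/3) = 18,328 and 9,242·1.15^(4/3) = 11,135. Power is 76.2% or 73.3%.

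**Dependence on effective size and follow-up.** A 5% loss in both arms takes 20,000 vs 13,000 to 79.4% (arcsine), and a 10% loss to 77.2%. With 0.75 person-years per patient, pooled-z power is about 66% for both pairs.

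**The case against.** The strongest reply is that the operative criterion is already the power condition. The Abstract repeats it without any count, and Section 8.5 says its estimates are for information and that the final size will change. On that reading 15,000 is a worked example. This does not remove the problem: the sentence in Section 8.7.2.4 says the patients will be needed, which is a requirement, and the caveat belongs to Section 8.5.

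Several limits do stand:
- **Reach.** A reader might infer that the count misleads whenever the arms differ in size. It does not. At 20,000 vs 23,000 both arms exceed 15,000 and the contrast rightly passes. The anti-epileptic cohort is expected to be at least as large as the erenumab cohort. Every projected cohort clears the stroke count of 3,750.
- **Certainty.** A reader might infer that the contrast plainly meets 80% power. That depends on the formula: pooled z and log risk ratio fall short. The arcsine formula fits the MI row and both counts, but not the stroke row of Table 3 at the stated 0.60 per 100 person-years (it gives 1.50, 1.43, 1.39 and 1.35 against 1.58, 1.51, 1.46 and 1.41 printed).
- **Projection and weighting.** The stated growth rate does not bring 9,242 users to 13,000, and trimming and weighting will reduce effective size. With smaller cohorts the contrast could properly fail a power rule too. This weakens the claim that a sound contrast is lost, but the 15,000 figure ignores the same losses.
- **Table 3.** A reader might infer that its MI row is wrong. It is correct for the equal cohorts it declares.

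**Conclusion.** The point holds in a limited form. The 15,000 count stands in for a criterion that depends on both arms. At the protocol's own projections it would exclude erenumab vs onabotulinumtoxinA for MI while admitting 15,000 vs 15,000, a pair of about equal or slightly lower power: 2.0 points lower by the arcsine formula, 0.8 lower by pooled z, 0.7 higher by log risk ratio. Nothing in these figures justifies treating the two pairs differently.

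The documents do not support saying that the contrast is adequately powered beyond doubt. The result is borderline and rests on one person-year per patient, a two-sided test, no loss to trimming or weighting, and 13,000 onabotulinumtoxinA users. The descriptive MI incidence in that cohort, its stroke contrast and the other MI contrasts are not affected at the projected sizes. The change is worth making because it bears on whether a planned safety comparison is run.

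**What to change.** In Section 8.7.2.4, replace the fixed counts by the criterion they stand for: each MI or stroke contrast proceeds, as far as size is concerned, when power to detect a risk ratio of 2.0 is at least 80%. Compute it by one named formula from the actual sizes of both arms after trimming, preferably using effective sizes after weighting and the observed person-time. Keep 15,000/15,000 and 3,750/3,750 as equal-arm illustrations only.

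Optionally, add the planned unequal pairs to Table 3: 20,000 vs 13,000 (MI about 1.98) and 20,000 vs 23,000 (MI about 1.82).

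The cost is protocol wording and one short calculation per contrast, with no extra data. The condition is then no longer a single number, and the onabotulinumtoxinA MI contrast may still fail if the actual cohorts are smaller than projected.
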